10 DATA AND SAFETY MONITORING PLAN

10.1 Adverse Events and Serious Adverse Events

10.1.1 Definition of Adverse Events (AE)

An adverse event will be considered any undesirable sign, symptom, medical, or psychological condition even if the event is not considered to be related to the investigational drug/intervention. Medical condition/diseases present before starting the investigational drug/intervention will be considered adverse events only if they worsen after starting study treatment/intervention. An adverse event is also any undesirable and unintended effect of research occurring in human subjects as a result of the collection of identifiable private information under the research. Adverse events also include any problems associated with the use of an investigational drug that adversely affects the rights, safety or welfare of subjects.

10.1.2 Definition of Serious Adverse Events (SAE)

An adverse event (AE) is considered a serious adverse reaction (SAE) if, in the view of either the investigator or sponsor, it results in any of the following outcomes:

- death,
- a life-threatening adverse event,
- inpatient hospitalization or prolongation of existing hospitalization,
- a persistent or significant incapacity or substantial disruption of the ability to conduct normal life functions, or
- a congenital anomaly/birth defect

Important medical events that may not result in death, be life-threatening, or require hospitalization may be considered serious when, based upon appropriate medical judgment, they may jeopardize the participant and may require medical or surgical intervention to prevent one of the outcomes listed in this definition. Examples of such medical events include allergic bronchospasm requiring intensive treatment in an emergency room or at home, blood dyscrasias or convulsions that do not result in inpatient hospitalization, or the development of drug dependency or drug abuse.

10.1.3 Classification of an Adverse Event

10.1.3.1 Severity of Event

For AEs not included in the protocol defined grading system, the following guidelines will be used to describe severity.

- **Mild** – Events require minimal or no treatment and do not interfere with the participant's daily activities.
- **Moderate** – Events result in a low level of inconvenience or concern with the therapeutic measures. Moderate events may cause some interference with functioning.
- **Severe** – Events interrupt a participant's usual daily activity and may require systemic drug therapy or other treatment. Severe events are usually potentially life-threatening or incapacitating. Of note, the term "severe" does not necessarily equate to "serious".

10.1.3.2 Relationship to Study Intervention

All AEs must have their relationship to study intervention assessed by the clinician who examines and evaluates the participant based on temporal relationship and his/her clinical judgment. The degree of certainty about causality will be graded using the categories below. In a clinical trial, the study product must always be suspect.

- **Definitely Related** – There is clear evidence to suggest a causal relationship, and other possible contributing factors can be ruled out. The clinical event, including an abnormal laboratory test result, occurs in a plausible time relationship to study intervention administration and cannot be explained by concurrent disease or other drugs or chemicals.
- **Probably Related** – There is evidence to suggest a causal relationship, and the influence of other factors is unlikely. The clinical event, including an abnormal laboratory test result, occurs within a reasonable time after administration of the study intervention, is unlikely to be attributed to concurrent disease or other

drugs or chemicals, and follows a clinically reasonable response on withdrawal (dechallenge).

- **Possibly Related** – There is some evidence to suggest a causal relationship (e.g., the event occurred within a reasonable time after administration of the trial medication). However, other factors may have contributed to the event (e.g., the participant's clinical condition, other concomitant events). Although an AE may rate only as "possibly related" soon after discovery, it can be flagged as requiring more information and later be upgraded to "probably related" or "definitely related", as appropriate.
- **Unlikely to be related** – A clinical event, including an abnormal laboratory test result, whose temporal relationship to study intervention administration makes a causal relationship improbable (e.g., the event did not occur within a reasonable time after administration of the study intervention) and in which other drugs or chemicals or underlying disease provides plausible explanations (e.g., the participant's clinical condition, other concomitant treatments).
- **Not Related** – The AE is completely independent of study intervention administration, and/or evidence exists that the event is definitely related to another etiology. There must be an alternative, definitive etiology documented by the clinician.

10.1.3.3 Expectedness

The PI will be responsible for determining whether an AE is expected or unexpected. An AE will be considered unexpected if the nature, severity, or frequency of the event is not consistent with the risk information previously described for the study intervention.

10.1.4 Time Period and Frequency for Event Assessment and Follow-Up

The occurrence of an AE or SAE may come to the attention of study personnel during study visits and interviews of a study participant presenting for medical care.

All AEs including local and systemic reactions not meeting the criteria for SAEs will be captured on the appropriate case report form (CRF). Information to be collected includes event description, time of onset, clinician's assessment of severity, relationship to study product (assessed only by those with the training and authority to make a diagnosis), and time of resolution/stabilization of the event. All AEs occurring while on study must be documented appropriately regardless of relationship. All AEs will be followed to adequate resolution.

Any medical condition (including a laboratory abnormality) that is present at the time that the participant is screened will be considered as baseline and not reported as an AE. However, if the study participant's condition deteriorates at any time during the study, it will be recorded as an AE.

Changes in the severity of an AE will be documented to allow an assessment of the duration of the event at each level of severity to be performed. AEs characterized as intermittent require documentation of onset and duration of each episode.

10.1.5 Adverse Event Reporting

AEs must be recorded into the case report forms per the following guidelines (Table 1).

Table 1

Type of Event	To whom will it be reported:	Time Frame for Reporting	How reported?
Any internal event resulting in death that is deemed DEFINITELY related to (caused by) study participation An internal event is one that occurs in a subject enrolled in a UVa protocol	IRB-HSR	Within 24 hours	IRB Online and phone call www.irb.virginia.edu/
Internal, Serious, Unexpected adverse event	IRB-HSR	Within 7 calendar days from the time the study team received knowledge of the event. Timeline includes submission of signed hardcopy of AE form.	IRB Online www.irb.virginia.edu/
Unanticipated Problems that are not adverse events or protocol deviations This might include a Data Breach.	IRB-HSR	Within 7 calendar days from the time the study team received knowledge of the event.	Unanticipated Problem report form. Unanticipated Problem Report Form
Protocol Deviations/Noncompliance The IRB-HSR only requires that MAJOR deviations be reported, unless otherwise required by your sponsor, if applicable.	IRB-HSR	Within 7 calendar days from the time the study team received knowledge of the event.	Protocol Deviation, Noncompliance and Protocol Exception Reporting Form Protocol Deviation Protocol Exception Reporting Form
Data Breach	The UVa Corporate Compliance and Privacy Office ITC: if breach involves electronic data	As soon as possible and no later than 24 hours from the time the incident is identified. As soon as possible and no later than 24 hours from the	UVa Corporate Compliance and Privacy Office- [contact] ITC: Information Security Incident Reporting procedure ,

	
Police if breach includes items that are stolen:
 
Stolen on UVA Grounds
 
OR
 
Stolen off UVA Grounds- contact police department of jurisdiction of last known location of PHI
	
time the incident is identified.
 
IMMEDIATELY.
	
https://security.virginia.edu/report-information-security-incident

--	---	---	--

UVA PI HELD IND

Life-threatening and/or fatal unexpected events related or possibly related to the use of the investigational agent.	FDA	Within 7 calendar days of the study team learning of the event	Form FDA 3500A (MedWatch) or narrative
Serious, unexpected and related or possibly related adverse events	FDA	Within 15 calendar days after the study team receives knowledge of the event	Form FDA 3500A (MedWatch) or narrative
All adverse events	FDA	Annually	IND annual report

10.2 Unanticipated Problems

10.2.1 Definition of Unanticipated Problems (UP)

The Office for Human Research Protections (OHRP) considers unanticipated problems (UPs) (may include a data breach) involving risks to participants or others to include, in general, any incident, experience, or outcome that meets all of the following criteria:

- Unexpected in terms of nature, severity, or frequency given the research procedures that are described in the protocol-related documents, such as the Institutional Review Board (IRB)-approved research protocol and informed consent document; and (b) the characteristics of the participant population being studied;
- Related or possibly related to participation in the research (“possibly related” means there is a reasonable possibility that the incident, experience, or outcome may have been caused by the procedures involved in the research); and
- Suggests that the research places participants or others at a greater risk of harm (including physical, psychological, economic, or social harm) than was previously known or recognized.

11 STATISTICAL CONSIDERATIONS

11.1 Statistical Hypotheses

Outcomes between the two groups will be compared and in a within-subject analysis will be performed given the crossover design. A descriptive analysis of the variables will be performed by calculating mean and standard deviation (SD), as appropriate, and absolute and percentage frequency. Differences between pre- and post-treatment scores (delta scores) will be assessed with the Wilcoxon signed-rank test. Correlations between delta scores and the variables considered [age, gender, body mass index (BMI), radiographic features] will be evaluated with the Spearman, Mann-Whitney, and Kruskal-Wallis tests. The significance threshold will be set at 0.05.

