
To determine the safety of treatment CBD.
	
Safety will be determined by evaluating:
 
 • The frequency and severity of adverse events from the beginning of treatment through the end of study participation. • Changes in skin appearance from baseline using standardized skin assessment tool. (patient will be removed from study with a score ≥ 2) • Clinically significant change in CBC (baseline and follow-up) • Clinically significant change in basic metabolic panel (i.e., BUN, creatinine, CO₂, Cl, K, Na, and glucose) (baseline and weekly follow-up) • Clinically significant change in hepatic function testing (i.e., serum transaminases [ALT/AST], total bilirubin, and alkaline phosphatase) (baseline and weekly follow-up) • Clinically significant change in vital sign assessments (i.e., heart rate and blood pressure) (baseline and weekly follow-up) • Suicidal behavior and thoughts as a specific question using the Columbia-Suicide Severity Rating Scale (C-SSRS) (baseline and weekly follow-up)
--	--

Study Population: 40 subjects with presenting with thumb basal joint arthritis over the age of 18 will be recruited from the UVA Hand Center.

Description of Sites/Facilities This will be a single-site study conducted at the UVA Hand Center at the University of Virginia.

Enrolling**Participants:****Description of****Study****Intervention:**

[figure not shown]
The study design will be a double-blind randomized control trial with crossover. Treatment will be blinded to the subjects and investigators. Patients will be randomly assigned two (2) weeks of the case (CBD) or control cream and then crossover to the other cream for two (2) additional weeks. Patients will apply the topical cream at their thumb basal joint twice daily for 1 hour. The subjects will be advised to observe for physiologic changes, skin changes, or other adverse effects. If mild to serious adverse events are noticed, the creams will be removed immediately and appropriate care and observation will be taken. Each condition will last for 2 weeks and then subjects will be contacted by the study coordinator to facilitate crossover into the other condition. To capture any delayed-onset adverse events, including those related to skin changes that might develop after the drug is discontinued, subjects will attend a follow-up visit seven (7) days following the last dose of investigational cream.

Study**Duration:****Participant****Duration:**

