4 OBJECTIVES AND ENDPOINTS

Objectives	Endpoints
Primary	
To determine therapeutic potential of CDB as a topical	Hand Functional Assessment: Change from baseline in hand functional assessment including grip, appositional,

treatment for thumb basal joint arthritis.	
and oppositional pinch strength (kg); Kapandji score; and MP and IP range of motion.
 
Patient Reported Outcome Measures: Change from baseline in the PROMIS-29 (Patient-Reported Outcomes Measurement Information System) and PROMIS upper extremity tests. The PROMIS-29 is a free publicly available generic health related quality of life (HRQoL) measure consisting of indices of pain, pain interference, depression, anxiety, global function, and social interactions. The PROMIS upper extremity test utilizes item-response theory and Computer Adaptive Test to efficiently and precisely report patient symptoms and perceived function.

Secondary	
To determine the safety of treatment CBD.
 
Safety will be determined by evaluating:
 
 • The frequency and severity of adverse events from the beginning of treatment through the end of study participation. • Changes in skin appearance from baseline using standardized skin assessment tool (patient will be removed from study with a score ≥ 2) • Clinically significant change in CBC (baseline and weekly follow-up) • Clinically significant change in basic metabolic panel (i.e., BUN, creatinine, CO₂, Cl, K, Na, and glucose) (baseline and weekly follow-up) • Clinically significant change in hepatic function testing (i.e., serum transaminases [ALT/AST], total bilirubin, and alkaline phosphatase) (baseline and weekly follow-up) • Clinically significant change in vital sign assessments (i.e., heart rate and blood pressure) • Suicidal behavior and thoughts as a specific question using the Columbia-Suicide Severity Rating Scale (C-SSRS) at baseline and follow-up.

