9 STUDY ASSESSMENTS AND PROCEDURES

9.1 Clinical Assessments

Hand Functional Assessment: Hand functional assessment will include grip, appositional, and oppositional pinch strength (kg); Kapandji score; and MP and IP range of motion. Assessments will be performed at Baseline and study Days 7, 14, 21, and 28.

Patient Reported Outcome Measures: The PROMIS-29 and PROMIS upper extremity tests will be collected. The PROMIS-29 is a free publicly available generic HRQoL measure consisting of indices of pain, pain interference, depression, anxiety, global function, and social interactions (Attachment 1, Appendix 14.4) Subjects will complete the measure at Baseline and study Days 7, 14, 21, and 28. The PROMIS upper extremity test utilizes item-response theory and Computer Adaptive Test to efficiently and precisely report patient symptoms and perceived function. Subjects will complete the measure in clinic using an iPad. The PROMIS upper extremity assessment is provided in Attachment 2 (Appendix 14.4). Subjects will complete the PROMIS assessment at Baseline and study Days 7, 14, 21, and 28.

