11.2 Sample Size Determination

Based on a 95% confidence interval to show a 50% reduction effect (as shown in the literature) and receive 80% power with a population variance of 0.25, sample size analysis resulted in a sample size of at least 16. The UVA Hand Center performed 421 operative procedures in 2018 for the management of thumb basal joint arthritis among our 6 fellowship trained hand surgeons, and consequently has a volume sufficient to accrue 40 patients during the study period.

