11.2.1 Randomization

The study participants will be randomized to either the treatment group or placebo group (1:1 ratio) once consent is signed and inclusion/exclusion criteria are satisfied. Randomization will be not be stratified. All investigators and subjects will be blinded.

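### The between-group comparison appears to rest on raw change from baseline; adjusting the first-period (Day 14) comparison for the Day 0 score would cut its variance by (1 − ρ)/2, with no new data

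*Combined protocol and SAP*

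**What the plan says.** Section 11.1 plans two efficacy comparisons in one sentence: "Outcomes between the two groups will be compared and in a within-subject analysis will be performed given the crossover design". The only analysis variable it defines is the pre-to-post difference (delta score). The only test it names for that variable is the Wilcoxon signed-rank test, which is paired. Delta scores are also to be related to age, gender, BMI and radiographic features; the baseline score is not in that list. No baseline-adjusted analysis appears anywhere.

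Section 4 words the efficacy endpoints as changes, for example "Change from baseline in hand functional assessment including grip, appositional", and does the same for the PROMIS measures. Section 9.1 says of hand function: "Assessments will be performed at Baseline and study Days 7, 14, 21, and 28". PROMIS follows the same days, and the Schedule of Activities (14.1) places the baseline assessment at Day 0.

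On size and allocation, the Synopsis says "40 subjects with presenting with thumb basal joint arthritis over the age of 18 will be recruited". Allocation is 1:1, and Section 11.2.1 adds: "Randomization will be not be stratified".

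**The concern.** A change score subtracts the whole of the baseline value. Unless baseline and follow-up are almost perfectly correlated, that subtracts too much and adds noise. ANCOVA estimates how much of the baseline to remove. It is therefore more precise, and it also takes out any chance difference between the groups at Day 0. With about 20 per sequence and no stratification, nothing in the design limits such a difference.

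The first-period comparison is worth protecting. Section 5.1 and the schedule move subjects from one cream to the other at Day 14 with no washout, so Day 0 to Day 14 is the only efficacy contrast that earlier CBD cannot affect. Under Sections 8.2 and 8.3, stopping treatment ends study participation, and treated subjects who leave are not replaced. Someone who leaves after period 1 can contribute only to this comparison, or to a model that keeps subjects with one period.

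**Working it through.** **Inputs from the documents**
- 40 subjects, 1:1, so about 20 per sequence (Synopsis, Section 11.2.1).
- "The significance threshold will be set at 0.05" (Section 11.1); taken as two-sided, which the plan does not say.
- The sample size basis is "to show a 50% reduction effect (as shown in the literature) and receive 80% power with a population variance of 0.25" (Section 11.2).

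**Inputs assumed, not in the documents**
- Day 0 to Day 14 correlation ρ: 0.3 to 0.7 as the main range, with 0.8 and 0.9 shown as well.
- True difference of 0.7 outcome SD.
- Equal SD at Day 0 and Day 14.

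**Step 1: the plan's own figure.** Section 11.2 reports that "sample size analysis resulted in a sample size of at least 16". Read the effect as a difference of 0.5 and the SD as √0.25 = 0.5. For two independent groups, n = 2 × (1.96 + 0.84)² × 0.25 / 0.5² = 15.7, so 16 per group. A paired formula with variance 0.25 per score and zero correlation also gives 15.7, so 16 in total. The figure reproduces, but it does not show which comparison it was meant for.

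**Step 2: variance of the first-period comparison.** In units of the outcome variance:
- change score: 2(1 − ρ)
- ANCOVA: 1 − ρ²
- ratio (ANCOVA to change): (1 + ρ)/2, so the reduction is (1 − ρ)/2
- estimating the slope with 40 subjects multiplies the ANCOVA variance by 1 + 1/36, about 3%

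| ρ (assumed) | Change | ANCOVA | Reduction | Reduction after slope cost |
|---|---|---|---|---|
| 0.3 | 1.40 | 0.91 | 35% | 33% |
| 0.5 | 1.00 | 0.75 | 25% | 23% |
| 0.7 | 0.60 | 0.51 | 15% | 13% |
| 0.8 | 0.40 | 0.36 | 10% | 8% |
| 0.9 | 0.20 | 0.19 | 5% | 2% |

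A simulation with 20 per sequence (10,000 runs per ρ) gave reductions of 33%, 23% and 12% at ρ = 0.3, 0.5 and 0.7.

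**Step 3: power, 20 v 20, two-sided 0.05, difference 0.7 SD.** The change score is tested on 38 degrees of freedom. ANCOVA is tested on 37, with the slope cost included.

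| ρ | Change score | ANCOVA |
|---|---|---|
| 0.3 | 45% | 61% |
| 0.5 | 58% | 69% |
| 0.7 | 80% | 85% |
| 0.8 | 93% | 94% |

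**Step 4: chance imbalance.** The standard error of the Day 0 difference is √(2/20) = 0.32 SD. A difference of that size shifts the expected change-score contrast by (1 − ρ) × 0.32, which is 0.16 SD at ρ = 0.5. Linear adjustment for Day 0 removes this shift.

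**Step 5: the within-subject contrast.** With one common baseline B, (Y₁ − B) − (Y₂ − B) = Y₁ − Y₂. The baseline cancels, so there is nothing to gain. In simulation, adding Day 0 as a covariate raised the variance of this contrast by about 3%. Without carryover and with equal correlations, its variance is 2(1 − ρ)/40, against 4(1 − ρ)/20 for the first-period change-score comparison: one quarter. At ρ = 0.5 that is 0.025 against 0.100.

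**The case against.** The strongest objection is that the plan never says the between-group comparison uses raw first-period change. Section 11.1 leaves its test, scale, time point and period open. The one test named for delta scores is paired, and the two groups could mean the two conditions. On that view the visible defect is an unspecified comparison, not a poor estimator. This stands as a limit: raw change is inferred from the endpoint wording, and a reader should not take it as stated. It does not remove the point, because change from baseline is the only efficacy scale the documents define, and an open choice needs the same sentence to close it.

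Second, the size rests on assumptions. The same measures are repeated in the same hands 14 days apart, so a correlation above 0.7 cannot be excluded, and the gain there is small. The 0.7 SD effect is also assumed. Section 11.2, read as in Step 1 with 0.5 as the outcome SD, implies 1.0 SD. Power would then go from 87% to 94% at ρ = 0.5 and from 98% to 99% at ρ = 0.7, after the slope cost. This stands in full.

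Third, a reader might infer that the crossover analysis itself loses precision, or that change scores bias the result. Neither follows. The baseline cancels in complete pairs, and change scores remain unbiased under randomization. The absent crossover model (period, sequence) is a larger gap, but a separate one that this change does not close.

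**Conclusion.** The point holds for the first-period between-group comparison, and only there. If that comparison uses raw change, as the endpoint wording suggests, ANCOVA on Day 0 is the better method. Its variance is lower by about 33%, 23% and 13% at ρ = 0.3, 0.5 and 0.7 after the slope cost, falling to about 8% to 2% at ρ = 0.8 to 0.9, and chance baseline imbalance is removed. The power gain at 0.7 SD is 16, 11 and 5 percentage points over the main range. These figures assume ρ, the effect size, equal variances, and all 40 subjects contributing; dropout would make the slope cost slightly larger. The change should be made because it is cheap and protects the one contrast free of carryover. It improves a supporting analysis and does not call the within-subject result into question.

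**What to change.** Add to Section 11.1: *The between-group comparison is a supporting analysis of the Day 14 score, CBD-first versus control-first, by ANCOVA with the Day 0 score as covariate, reporting the adjusted difference and its 95% confidence interval.*

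For ordinal scores such as Kapandji, a rank-based ANCOVA may be added as a sensitivity test. It should be reported as a p-value only, because it does not yield an adjusted difference on the original scale.

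The cost is one sentence of analysis wording, one degree of freedom and about 3% of variance. The Day 0 scores are already in the schedule, so no new data are needed.
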